# PROTOCOL SYNOPSIS

Protocol Title:	A Phase 2, Open-Label, Multi-Dose, Dose Escalation Trial to Evaluate the Safety, Tolerability, Pharmacokinetics, and Pharmacodynamics of Intravenous Infusions of ALN-TTR02 in Patients with TTR Amyloidosis
Indication:	Treatment of patients with transthyretin (TTR)-mediated amyloidosis (ATTR)
Protocol Number:	ALN-TTR02-002
Phase of Development:	2
Design:	Multi-center, multi-national, open-label, multi-dose, dose escalation study.
	Consented patients meeting the eligibility criteria will be enrolled into sequential cohorts of increasing doses of ALN-TTR02, the investigational drug. Each cohort will comprise 3 patients, who are to receive 2 intravenous (IV) infusions of ALN-TTR02, 4 weeks apart.
	A Safety Review Committee (SRC) will evaluate safety in the study and determine if it remains acceptable to continue dosing per their safety review charter. To ensure timely safety information exchange across the participating study centers, the SRC will be comprised of all Principal Investigators (PIs) participating in the study or their designee, the Alnylam Medical Monitor, and the Contract Research Organization (CRO) Medical Monitor.
	The dosing of cohorts will be as follows:
	• Dosing within a cohort: The first patient will receive their first dose and if the dose is well tolerated, per Section 5.7.3 (Dose-limiting Toxicity), Patients 2 and 3 will receive their first dose at that same dose level no sooner than 48 hours apart, with Patient 2 receiving a dose of study drug no sooner than 48 hours after the dosing of Patient 1. Similar to the first dose, the second dose will be administered to patients 4 weeks after the first dose in a sequential manner with at least 48 hours separating dosing of each patient.
	Dosing of the next cohort: Collective cohort safety and tolerability data on Patients 1 to 3 through at least

	96 hours post-first dose will be reviewed by the SRC; if the administered dose is found to be safe and well tolerated, dosing for the next cohort will begin no sooner than 96 hours after Patient 3 had safely received dose 1 from the previous cohort. Patients in the cohort would be dosed and reviewed for safety and tolerability following the same procedures as used for other cohorts (as stated above). For patients on all dose levels other than the starting dose level of 10 µg/kg, prior to receiving the second dose, the SRC will review the cumulative safety and tolerability data of at least 2 patients from the previous dose level(s) with at least 96 hours of follow-up after
	receiving a second dose of study drug.
	The SRC will also be convened in the event of any potential dose-limiting toxicity (DLT) to determine whether stopping rules have been met.
Study Sites	This study is planned to be conducted at up to 10 study centers worldwide.
Investigational Drug:	ALN-TTR02 is comprised of drug substance ALN-18328 (small interfering ribonucleic acid [siRNA] targeting wild type TTR messenger ribonucleic acid [mRNA] as well as all TTR mutations) formulated in a lipid nanoparticle (LNP) containing the following lipid excipients: DLin-MC3-DMA, PEG 2000 -C-DMG, DSPC, and cholesterol.
Control Drug:	Not applicable.
Dosage, Route of Administration and Duration of Treatment of Investigational Drug:	Four cohorts are planned to be enrolled to evaluate 2 consecutive doses, 4 weeks apart of the following dose levels: 10, 50, 150, and 300 µg/kg ALN-TTR02. Based on the interim evaluation of safety data, it may also be decided by the SRC that an optional cohort may be utilized which will include 3 additional patients. Dosing in these optional cohorts may occur at a previously tested dose that was found to be safe and where stopping rules were not met or at an intermediate dose level. Patients in the optional cohort would be dosed and reviewed for safety and tolerability following the same procedures as used for other cohorts. Optional cohort(s) would be included to further confirm the safety and/or pharmacodynamic (PD) effect of previously evaluated dose levels, which may include evaluation of the original dosing regimen (once every 4 weeks), an alternative dosing regimen (once every 3 weeks), and/or an alternative

Amendment 2.1 Confidential Page 9 of 116

premedication regimen and infusion rate. The dosing regimen for the first optional cohort will be once every 4 weeks, and the dosing regimen for the remaining 4 optional cohorts will be once every 3 or 4 weeks. It is anticipated that the first 2 optional cohorts will use the original premedication regimen, and the remaining 3 optional cohorts may be used to explore the alternative premedication regimen and infusion rate.

The SRC will review all available safety data and make recommendations on dosing and premedication regimens prior to dosing of any of the optional cohorts.

The Independent Ethics Committees (IECs) will be informed of the implementation of optional cohorts. Up to 5 optional cohorts are permitted in this study.

Patients receiving the original premedication regimen will be administered the following prior to each dose of ALN-TTR02:

- Oral (PO) dexamethasone (8 mg) or equivalent administered the evening before dosing and 20 mg 30 to 60 minutes prior to start of infusion of ALN-TTR02;
- Oral paracetamol (500 mg) or equivalent the evening before dosing and 30 to 60 minutes prior to the start of infusion of ALN-TTR02;
- Oral H2 blocker (e.g., ranitidine 150 mg or famotidine 20 mg or equivalent other H2 blocker dose) the evening before dosing and 30 to 60 minutes prior to start of infusion of ALN-TTR02; and
- Oral H1 blocker, 10 mg cetirizine or equivalent (hydroxyzine 25 mg or fexofenadine may be substituted if patient does not tolerate cetirizine) the evening before dosing and 30 to 60 minutes prior to start of infusion of ALN-TTR02.

The alternative premedication regimen that can be used in select optional cohorts, as agreed upon by the SRC, will be administered prior to each dose of ALN-TTR02 and includes the following:

• Intravenous (IV) dexamethasone (10 mg) or equivalent, administered at least 60 minutes prior to the start of infusion of ALN-TTR02;

- Oral paracetamol (500 mg) or equivalent at least 60 minutes prior to the start of infusion of ALN-TTR02;
- Intravenous H2 blocker (e.g., ranitidine 50 mg, famotidine 20 mg, or equivalent other H2 blocker dose) at least 60 minutes prior to start of infusion of ALN-TTR02; and
- Intravenous H1 blocker: diphenhydramine 50 mg IV (or equivalent other IV H1 blocker available at the study site) at least 60 minutes prior to start of infusion of ALN-TTR02. Hydroxyzine or fexofenadine 25 mg PO or cetirizine 10 mg PO may be substituted for any patient who does not tolerate IV diphenhydramine or other IV H1 blocker.

For patients receiving the original premedication regimen and infusion rate, doses of ALN-TTR02 will be administered IV over 60 minutes by a controlled infusion device at a flow rate of approximately 3.3 mL/min.

For patients enrolled in the optional cohorts evaluating the alternative premedication regimen and infusion rate, the flow rate of ALN-TTR02 will be approximately 1.1 mL/min during the first 15 minutes (1/3rd the original flow rate) with the remainder of the infusion administered at a flow rate of 3.3 mL/min for a total infusion time of approximately 70 minutes.

The infusion time may be extended up to 3 hours in the event of a mild or moderate infusion reaction (study drug administration will not be resumed for any patient following a severe infusion reaction).

Patients will remain hospitalized at the study site for at least 24 hours following completion of dosing on Days 0 and 28, for safety assessments and pharmacokinetic (PK) sampling.

Time on Study	The duration of patient participation in this study is approximately 36 weeks (screening [up to 45 days prior to study drug administration] through Day 208).
	An open-label extension study at the recommended Phase 3 dose and regimen (as derived from Study ALN-TTR02-002) is planned, which will enable the patients who enrolled in Study ALN-TTR02-002 to receive additional, long-term dosing and safety follow-up. For some of the patients, this may preclude the completion of all of the follow-up period assessments of Study ALN-TTR02-002 if they are deemed eligible to participate in the extension study prior to completion of the full follow up through Day 208. Such patients will be followed up for a minimum of 28 days after their last dose in the current ALN-TTR02-002 study prior to being enrolled in the extension study. The extension study will be implemented only after dose escalation is completed in Study ALN-TTR02-002, with post second dose follow-up through Day 208 in at least 1 cohort at the highest dose.
	Note: A patient will be followed every 2 weeks after Day 56 until TTR levels have recovered to at least 80% of baseline.
	Evaluations will be performed as indicated in the schedule of assessments.
Primary Objective:	To evaluate the safety and tolerability of multiple doses of ALN-TTR02.
Secondary Objectives:	
 
To characterize the plasma and urine PK of ALN-TTR02.
 
To assess preliminary evidence of the PD effect of ALN-TTR02 on serum total TTR levels.
 

Sample Size:	Based on the entry criteria and the proposed dose escalation scheme, up to 27 patients are expected to be enrolled. Three patients are to be enrolled at each dose level and up to 5 optional cohorts of 3 patients each will be permitted.
Inclusion and	Each patient must meet the following criteria to be enrolled:
Exclusion Criteria:	1. Male or female aged 18 years or older.
	2. Patients has a biopsy-proven diagnosis of TTR amyloidosis with documented signs/symptoms of the disease (e.g., sensory, motor, or autonomic neuropathy) that are at least mild to moderate in severity.
	3. Body mass index (BMI) of 17–33 kg/m  .

Amendment 2.1 Confidential Page 12 of 116

- 4. Karnofsky performance status of 60% or greater.
- 5. Absolute neutrophil count (ANC) ≥1500 cells/mm³, platelet count ≥100,000 cells/mm³, and hemoglobin ≥10 g/dL.
- 6. Adequate liver function, demonstrated by an aspartate transaminase (AST) and alanine transaminase (ALT) ≤2.5 × the upper limit of normal (ULN), total bilirubin within normal limits, albumin >3 g/dL, international normalized ratio (INR) ≤1.2.
- 7. Adequate renal function: serum creatinine  $\leq 1.5 \times ULN$ .
- 8. Seronegative for hepatitis B virus (HBV) and hepatitis C virus (HCV).
- 9. Women of child-bearing potential must have a negative pregnancy test, cannot be breast feeding, and must be using two highly effective methods of contraception prior to screening, throughout study participation, and for 1 month after ending study participation. Highly effective methods of birth control are defined as: hormonal oral, implantable, injectable, or transdermal contraceptives in conjunction with spermicide, condom, or diaphragm; mechanical spermicide in conjunction with a barrier such as a condom or diaphragm; intrauterine device (IUD) in conjunction with spermicide or condom; or surgical sterilization of partner in conjunction with spermicide, condom, or diaphragm.
- 10. Males agree to use appropriate contraception throughout study participation and for 1 month after ending study participation.
- 11. Patient is willing and able to comply with protocolrequired visit schedule and visit requirements and provide written informed consent.

	12. Patients will be excluded if they meet any of the following criteria:
	13. Pregnant or nursing.
	14. Has had a liver transplant.
	15. Has a known surgery planned during any point of the study period.
	16. Has known human immunodeficiency virus (HIV) positive status.
	17. Has a known or suspected systemic bacterial, viral, parasitic, or fungal infection.
	18. Received an investigational agent, other than tafamidis or diflunisal, within 30 days prior to study drug administration.
	19. Has a New York Heart Association heart failure classification >2.
	20. Has unstable angina.
	21. Has uncontrolled clinically significant cardiac arrhythmia.
	22. Is considered unfit for the study by the Principal Investigator.
	23. Had a prior severe reaction to a liposomal product.
	24. Has known hypersensitivity to oligonucleotides.
	25. Is an employee or family member of Alnylam or the clinical study site personnel.
Pharmacodynamic Assessments:	The PD evaluation will include assessment of effects of ALN-TTR02 on serum total TTR levels.

Amendment 2.1 Confidential Page 14 of 116

Pharmacokinetic Assessments:	The PK evaluation will include plasma-concentration time profiles for ALN-18328 and the novel lipid components DLin-MC3-DMA and polyethylene glycol (PEG) 2000 -C-DMG. ALN-18328 concentration will be determined at specified time points post-dose. DLin-MC3-DMA and PEG 2000 -C-DMG concentrations will be determined at specified time points up to 180 days post- second dose. An assessment of plasma concentrations of free and encapsulated siRNA will be determined at specified time points.
	If the infusion of study drug is stopped and the site is considering restarting, a PK blood sample will be taken when the infusion is stopped.
	Urine will be collected to determine ALN-18328 excreted in urine and renal clearance (CL R ) of ALN-18328 after dosing with ALN-TTR02. In addition urine samples will be collected to quantify analytes that may include DLin-MC3-DMA and/or its metabolites at specified time points.
Safety Assessments:	26. Safety evaluations will include assessment of adverse events (AEs), electrocardiograms (ECGs), cardiac monitoring (telemetry), arterial oxygen saturation (SaO 2 ) using pulse oximetry, vital signs (blood pressure, pulse rate, oral body temperature, and respiration rate), clinical laboratory safety tests (hematology, serum chemistry, liver function tests, thyroid function parameters, serology, coagulation parameters, urinalysis, cytokines, C-reactive protein, complement factors), and physical examinations.
Other Assessments:	

27. Exploratory effects of ALN-TTR02 will be evaluated by:

28. Serial measurement of circulating mutant and wild type TTR levels

	
 
29. Serial measurement of circulating vitamin A and retinol binding protein (RBP) levels
 
Blood collections to explore the expression of hepatocyte derived proteins to further characterize the biological effects of siRNA LNPs.
 

Amendment 2.1 Confidential Page 15 of 116

Dose-Limiting	Dose-limiting toxicities will include any of the following:	
Toxicities and Stopping Criteria:	1. Any life-threatening toxicity.	
Stopping Criteria.	2. ALT and AST ≥5 × ULN or total bilirubin >2.0 mg/dL.	
	3. An infusion reaction that requires hospitalization, despite premedication.	
	4. Any other toxicity which in the opinion of the SRC precludes further dosing.	
	Stopping Rules:	
	For any DLT, accrual to that dose level will stop, all dosing will be discontinued, and dose escalation will end, pending further evaluation of all available safety data by the SRC.	
Statistical Methods:	Statistical analyses will be primarily descriptive in nature.  Adverse event summaries will include tabulations of all treatment-emergent AEs, treatment-related AEs, serious adverse events (SAEs), discontinuations due to AEs, and AEs of various grading severity. By-patient listings will be provided for deaths, SAEs, and AEs leading to discontinuation of treatment.	
	Descriptive statistics will be provided for clinical laboratory data, vital signs data, and ECG interval data, presented as both actual values and changes from baseline relative to each onstudy evaluation. Laboratory shift tables from baseline to worst values will be presented.	
	Pharmacokinetic analyses will be conducted using non-compartmental and/or compartmental evaluation of ALN-18328 (siRNA), DLin-MC3-DMA (lipid) and PEG 2000 -C-DMG (lipid) plasma concentration-time data to determine PK parameter estimates using a validated software program,	
	PK and PD data will be assessed descriptively whenever possible and by exploratory statistical comparisons.	

Amendment 2.1 Confidential Page 16 of 116

**Table 1-1:** Schedule of Assessments for Cohorts Administered ALN-TTR02 Once Every Four Weeks

	Screening	Pre-l	Dosing			Do	sing Cycl	es			I	Follow-Up	
							D 7	D 10	D 14	D 21			
		D -1	D 0	D 0	D 1	D 2	(±1 D)	(±2 D)	(±3 D)	(±3 D)			
	D -45 to		D 28	D 28	- 40	- 40	D 35	D 38	D 42	D 49	D 56 a	D 112	D 208 a
Procedures	D -3	D 27	(+2 D)	(+2 D)	D 29	D 30	(±1 D)	(±2 D)	(±3 D)	(±3 D)	(±3 D)	(±10 D)	(±2 W)
Informed Consent	X												
Demographics	X												
Medical History	X		X b										
Inclusion/Exclusion Criteria	X		X										
Physical Examination, excluding weight	X		X c		X c	X c			X c		X		
Weight	X		$X^d$										
Height	X												
Body Mass Index (BMI)	X		X										
Vital Signs e	X					X			X		X		
Vital Signs (Serial) f			X	X	X								
Echocardiogram g	X												
12-Lead ECG	X										X		
ECG (Serial) h			X	X	X								
Inpatient at Study Site			X	X	$X^{i}$								
Cardiac Monitoring (Telemetry) j			X	X	X								
Pulse Oximetry (Serial) f			X	X	X								
Serum Pregnancy Test (females only)	X										X		
Urine Pregnancy Test (females only) k			X										
Hepatitis B/C Status 	X												
Serum Chemistry, Hematology, Urinalysis	X		X m		X				X		X		

	Screening	Pre-	Dosing			Do	sing Cycl	es			ı	Follow-Up	
		D -1	D 0	D 0	D 1	D 2	D 7 (±1 D)	D 10 (±2 D)	D 14 (±3 D)	D 21 (±3 D)			
Procedures	D -45 to D -3	D 27	D 28 (+2 D)	D 28 (+2 D)	D 29	D 30	D 35 (±1 D)	D 38 (±2 D)	D 42 (±3 D)	D 49 (±3 D)	D 56 a (±3 D)	D 112 (±10 D)	D 208 a (±2 W)
Liver Function Tests n	X		X m		X	X	X		X		X		
Coagulation Studies o	X		X m		X								
Lipid Panel p			X										
TTR protein, Vitamin A, and RBP in serum	X		$X^q$		X	X	X	X	X	X	X r	X	X
TTR mRNA in serum	X		X		X	X							
Thyroid Function Tests s	X		$X^{m}$						X		X		
Complement Bb t			X	X	X								
If infusion reaction: Tryptase and C3a u				X	X								
Premedication v		X	X										
Premedication reminder w		X											
Study Drug Administration				$X^{x}$									
Anti-PEG Antibody Testing (IgG, IgM)	X		X				X				X		X
Cytokines and CRP y			X	X	X								
Plasma PK Sampling z			X	X	X	X	X		X	X	X	X	X
Urine PK Sampling aa			X	X	X	X	X		X	X	X	X	X
Exploratory Biomarkers	X		$X^{bb}$		X	X	X	X	X	X	X		
Concomitant Medications	X						Continuo	us Monito	ring				
Review/Record AEs									_				
Study Completion											X		

Footnotes on following pages.

Note: The schedule of assessments for optional cohorts administered ALN-TTR02 once every 3 weeks is provided in Appendix 4.

- a Early termination procedures: if a patient withdraws prior to Day 56, then the Days 56 and 208 visits should be performed. If a patient is withdrawn/withdraws after Day 56 and prior to Day 208, then the Day 208 visit should be performed.
- b Interval medical history.
- c Focused physical examination (includes head/ears/eyes/nose/throat [HEENT], cardiovascular, respiratory, abdominal, and hepatic assessments). If the screening physical examination was performed within 72 hours of Day 0, then the pre-dose (Day 0) physical examination does not need to be repeated; however, the patient's weight will be obtained.
- d Weight measured on Day 0 and Day 28 will be used for calculating first and second dose, respectively.
- e Vital signs to include: blood pressure, pulse rate, oral body temperature, and respiratory rate. Parameters are to be measured in the supine position using an automated instrument after the patient has rested comfortably for 10 minutes.
- f Serial measures (vital signs and pulse oximetry) are to be measured within 30 minutes pre-dose; at the end of infusion (EOI); and 30 (±5) minutes; 1, 2, and 3 (±15 minutes) hours; 6, 12, and 18 (±30 minutes) hours; and 24 (+30 minutes) hours post-infusion.
- g Not needed if a normal echocardiogram has been obtained within the past 90 days.
- h Serial electrocardiograms (ECGs) will be collected in 3 replicates within 30 minutes pre-dose, EOI, and 30 (±5) minutes, 2 and 4 (±15 minutes) hours, and 24 (+30 minutes) hours post-infusion.
- i Patients will be hospitalized at the study site for at least 24 hours after the end of infusion of study drug. Patients may be discharged upon completion of review by the Investigator of ECG, sodium, potassium, creatinine, albumin, calcium, glucose, phosphate, and LFTs results obtained at 24-hours post-infusion, if results are deemed not clinically significant. Any clinically significant findings must be discussed with the medical monitor to determine whether patient can be discharged and to formulate plans for patient follow-up.
- j Continuous cardiac monitoring will be performed via telemetry starting no later than 30 minutes prior to dosing and continuing through 24 hours (+1 hour) post-dose.
- k Day 0 pre-dose only, not performed on Day 28.
- l Serologies include hepatitis B surface antibody (HbsAb), hepatitis B surface antigen (HbsAg), and anti-hepatitis C virus antibody (anti-HCV Ab).
- If the parameter was assessed and meets eligibility requirements within 72 hours of Days 0 and 28, then it does not need to be repeated pre-dose (Days 0 and 28, respectively).
- n Liver function tests include aspartate transaminase (AST), alanine transaminase (ALT), alkaline phosphatase, and bilirubin (total and direct).
- o Coagulation studies include prothrombin time (PT), activated partial thromboplastin time (aPTT), and international normalized ratio (INR).
- p Lipid panel (non-fasting) includes total cholesterol, high density lipoprotein (HDL), low density lipoprotein (LDL), very low density lipoprotein (VLDL), and triglycerides will be collected on Day 0 only.
- q Pre-dose samples for TTR protein, vitamin A, and RBP measurements will be drawn immediately (within 10 minutes) prior to the premedications and immediately prior to dosing.
- r A patient will be followed approximately every 2 weeks after Day 56 if their TTR level continues to recover but is not found to have returned to within at least 80% of the baseline value. If this occurs, the patient will be followed and discussed at each SRC meeting until the TTR level returns to within at least 80% of the baseline value.
- s Thyroid function tests include thyroid stimulating hormone (TSH), thyroxine (T4), and triiodothyronine (T3).
- A blood sample will be collected for the assessment of complement Bb immediately (within 10 minutes) pre-dose, and 30 (±5) minutes, and 2 (± 15 minutes) and 24 hours (±120 minutes) post infusion. If the patient experiences an infusion reaction, a blood sample for analysis of complement factors should be obtained within 1 hour of the start of the reaction.

- A blood sample for the assessment of tryptase and C3a is to be collected only in the event of an acute infusion reaction: at time of event or as soon as possible after onset, 1 hour, and 24 hours after the event.
- v Premedications include dexamethasone (8 mg, or equivalent), paracetamol (500 mg, or equivalent), H2 blocker (e.g., 150 mg ranitidine or 20 mg famotidine, or equivalent other H2 blocker dose), and H1 blocker (10 mg cetirizine, 25 mg hydroxyzine, fexofenadine or equivalent may be substituted) will be self-administered per os (PO) the evening before study drug administration. Thirty to 60 minutes prior to the start of study drug infusion, dexamethasone (20 mg PO, or equivalent), paracetamol (500 mg PO, or equivalent), an H2 blocker (PO), and an H1 blocker (PO) will be administered by study site personnel. Patients enrolled in an optional cohort evaluating the use of an alternative premedication regimen, as agreed upon by the SRC, will receive the following medications at least 60 minutes prior to the start of infusion of ALN-TTR02: dexamethasone (10 mg IV, or equivalent), paracetamol (PO 500 mg; or equivalent), IV H2 blocker (e.g. ranitidine 50 mg, famotidine 20 mg, or equivalent other H2 blocker dose), and IV H1 blocker (e.g., diphenhydramine 50 mg or equivalent; hydroxyzine or fexofenadine 25 mg PO or cetirizine 10 mg PO may be substituted for any patient who does not tolerate IV diphenhydramine or other IV H1 blockers). These patients will not receive any premedications the evening prior to ALN-TTR02 dosing.
- w Site personnel are to call patients the day before dosing to remind them to take premedications that evening (the day before dosing). This reminder will not be needed for patients enrolled in optional cohorts evaluating the alternative premedication regimen.
- x The infusion site will be assessed for any localized reaction pre-dose, during infusion, and for 30 minutes after the infusion.
- y A blood sample for the assessment of cytokines and C-reactive protein (CRP) will be collected immediately (within 10 minutes) pre-dose, and 2 (±15 minutes), 6 (±15 minutes), and 24 hours (±120 minutes) post infusion. If the patient experiences an infusion reaction, a blood sample for analysis of cytokines should be obtained within 1 hour of the start of the reaction.
- z For each dose, plasma PK samples (siRNA and lipids) will be collected pre-dose (within 1 hour of planned dosing start), EOI, and then 5, 10, and 30 minutes, and 1, 2, 4, 6, 24 and 48 hours post infusion. Samples will also be collected on Days 7, 14, 21, 35, 42, 49, 56, 112, and 208. Plasma PK on Day 0 at EOI and then 2 hours post-infusion will be analyzed for both free and encapsulated siRNA for cohort 3 and onward, including any optional cohorts. For each post dose PK blood draw, the following sampling windows are allowed: ±1 minute for the 5- and 10-minute draws; ±2 minutes for the 30-minute draws; ±5 minutes for the 1-, 2-, 4-, and 6-hour draws; and ±120 minutes for the 24- and 48-hour draws.
- aa For each dose, urine PK samples will be collected pre-dose (within 1 hour of planned dosing start), and from 0-6 hours post-infusion (pooled). Samples will also be collected on Days 7, 14, 21, 35, 42, 49, 56, 112, and 208.
- bb Pre-dose samples should be collected prior to infusion, but after premedications have been administered.

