#### **6.3** Treatment Visits

# 6.3.1 Day 0 or Day 28 (+2 days); Day 0 or Day 21 for optional cohorts dosed once every 3 weeks

#### **6.3.1.1** Pre-dose

Patients who are determined to be eligible for the study, based on screening evaluations, will be enrolled on Day 0 and assigned to the appropriate dose cohort (see Section 4.4.1).

Patients will undergo the following procedures before study drug administration on Day 0 or Day 28 (Day 0 or Day 21 for optional cohorts dosed once every 3 weeks):

- Reassess study eligibility using the inclusion and exclusion criteria.
- Obtain updated medical history information.

- Conduct a focused physical examination (includes head/ears/eyes/nose/throat [HEENT], cardiovascular, respiratory, abdominal and hepatic assessments), including weight. If the screening physical examination was performed within 72 hours of Day 0, then it does not need to be repeated; however, the patient's weight will need to be obtained. For the first dose of study drug, this weight assessment (Day 0) will be used by the Pharmacy in the preparation of the patient's first dose.
  - o Calculate BMI.
  - Measure height.
- Perform a urine pregnancy test (women of child-bearing potential only), the results of which must be known prior to the administration of study drug.
- Obtain measurements of:
  - Vital signs
  - o Twelve-lead ECG.
  - Pulse oximetry.
- Collect blood samples for clinical laboratory tests (if the screening studies were performed within 72 hours of Day 0, then these laboratory tests need not be repeated), including:
  - Hematology.\*
  - Serum chemistries.\*
  - Liver function tests.\*
  - Coagulation studies.\*
  - Anti-PEG antibodies (IgG and IgM).
  - Thyroid function tests.\*
  - Lipid panel (Day 0 only).
  - o Complement Bb (within 10 minutes predose).
  - o Cytokines (within 10 minutes predose).
  - o CRP (within 10 minutes predose).

Note: those parameters marked with an asterisk do not have to be reassessed on Days 0 or 28 (Days 0 or 21 for optional cohorts dosed once every 3 weeks) if measures are obtained within 72 hours prior to dosing and meets eligibility criteria.

- Collect urine sample for urinalysis.\*
- Collect blood sample for PK pre-dose (within 1 hour of planned dosing start).

- Collect urine sample for PK pre-dose (within 1 hour of planned dosing start).
- Obtain concomitant medications information.

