## 7.2.7.8 Pregnancy Test

A serum pregnancy test will be performed for women of child-bearing potential at Screening, at the Day 56 study visit, and any time pregnancy is suspected. A urine pregnancy test will be performed pre-dose on Day 0 for women of child-bearing potential, the results of which must be known prior to administration of study drug. Patients who are pregnant are not eligible for study participation. Patients determined to be pregnant while on study will be followed until pregnancy outcome is known (see Section 8.12).

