- Patients will be hospitalized at the study site for at least 24 hours after the end of infusion of study drug. Patients may be discharged upon completion of review by the Investigator of ECG, sodium, potassium, creatinine, albumin, calcium, glucose, phosphate, and LFTs results obtained at 24-hours post-infusion, if results are deemed not clinically significant. Any clinically significant findings must be discussed with the medical monitor to determine whether patient can be discharged and to formulate plans for patient follow-up.
- Continuous cardiac monitoring will be performed via telemetry starting no later than 30 minutes prior to dosing and continuing through 24 hours (+1 hour) post-dose.
- k Day 0 pre-dose only, not performed on Day 21.
- 1 Serologies include hepatitis B surface antibody (HbsAb), hepatitis B surface antigen (HbsAg), and anti-hepatitis C virus antibody (anti-HCV Ab).
- m If the parameter was assessed and meets eligibility requirements within 72 hours of Days 0 and 21, then it does not need to be repeated pre-dose (Days 0 and 21, respectively).
- n Liver function tests include aspartate transaminase (AST), alanine transaminase (ALT), alkaline phosphatase, and bilirubin (total and direct).
- o Coagulation studies include prothrombin time (PT), activated partial thromboplastin time (aPTT), and international normalized ratio (INR).
- p Lipid panel (non-fasting) includes total cholesterol, high density lipoprotein (HDL), low density lipoprotein (LDL), very low density lipoprotein (VLDL), and triglycerides will be collected on Day 0 only.
- q Pre-dose samples for TTR protein, vitamin A, and RBP measurements will be drawn immediately (within 10 minutes) prior to the premedications and immediately prior to dosing.
- r A patient will be followed approximately every 2 weeks after Day 56 if their TTR level continues to recover but is not found to have returned to within at least 80% of the baseline value. If this occurs, the patient will be followed and discussed at each SRC meeting until the TTR level returns to within at least 80% of the baseline value.
- s Thyroid function tests include thyroid stimulating hormone (TSH), thyroxine (T4), and triiodothyronine (T3).

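### The protocol disagrees with itself on a urine pregnancy test before dose 2; under the schedule, the dose 2 eligibility re-check rests on a scheduled result three to four weeks old

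*Protocol*

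**What the plan says.** Section 6.3.1.1 opens its list with "Patients will undergo the following procedures before study drug administration on Day 0 or Day 28" and names Day 0 or Day 21 for the 3-week cohorts. One item reads "Perform a urine pregnancy test (women of child-bearing potential only), the results of which must be known prior to the administration of study drug". It carries no day limit. Another item in the list does: "Lipid panel (Day 0 only".

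The schedules say otherwise. Footnote k of Table 1-1 reads "Day 0 pre-dose only, not performed on Day 28", and footnote k of Table 12-1 reads "Day 0 pre-dose only, not performed on Day 21". The SAP reproduces both tables and both footnotes.

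Section 7.2.7.8 agrees with the schedules on the urine test: "A urine pregnancy test will be performed pre-dose on Day 0 for women of child-bearing potential". It places the serum test at Screening, "at the Day 56 study visit, and any time pregnancy is suspected". The synopsis, under Time on Study, adds "Evaluations will be performed as indicated in the schedule of assessments".

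Sections 5.6 and 6.3.1.2 make it mandatory to reassess eligibility before dose 2. Pregnancy is exclusion 1 in section 4.3, and a negative pregnancy test is part of the inclusion criteria in section 4.2.

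**The concern.** Two sites can each follow current protocol text and treat the same patient differently at dose 2. One has a pregnancy result from the dosing visit. The other relies on the Day 0 result, because no further test is scheduled until Day 56.

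Pregnancy is an eligibility criterion that can change between doses, and the protocol insists on a fresh eligibility check at that point. What is at stake is an avoidable exposure to study drug in an unrecognised pregnancy, in a trial whose section 1.6 expects no benefit to participants from the transient TTR lowering.

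**Working it through.** There is no planned figure to reproduce; the check is a comparison of texts followed by visit-day arithmetic.

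**Which texts point which way**

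| Source | Urine test before dose 2? |
|---|---|
| 6.3.1.1 pre-dose list | Yes, on its face |
| Table 1-1, footnote k | No (Day 28) |
| Table 12-1, footnote k | No (Day 21) |
| 7.2.7.8 | Names Day 0 only |
| 8.12, opening sentence | Ties ineligibility to a positive test at Screening or Day 0, which fits Day 0 only |

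No sentence says which source governs. The synopsis pointer to the schedule gives a site a reason to follow footnote k, but it is not a precedence rule.

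**Inputs**

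- Dose 2, 4-week cohorts: Day 28 (+2), so Day 28 to 30 (Table 1-1). Section 6.3.1.3 prints the window as ±2, which would give Day 26 to 30.
- Dose 2, 3-week cohorts: Day 21 (+2), so Day 21 to 23 (Table 12-1).
- Next scheduled pregnancy test: Day 56 (±3), so Day 53 to 59.

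**Age of the Day 0 result at dose 2** = dose 2 day − 0

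- 4-week: 28 to 30 days (26 to 30 with the ±2 window).
- 3-week: 21 to 23 days.

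**Time from dose 2 to the next scheduled test** = Day 56 visit day − dose 2 day

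- 4-week: nominally 56 − 28 = 28 days; range 53 − 30 = 23 to 59 − 28 = 31 days. With the ±2 window the upper end is 59 − 26 = 33.
- 3-week: nominally 56 − 21 = 35 days; range 53 − 23 = 30 to 59 − 21 = 38 days.

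**Comparison within the protocol.** Footnote m lets a site skip the pre-dose hematology, chemistry, urinalysis, liver, coagulation and thyroid tests only if they were done within 72 hours (3 days) of dosing and meet eligibility. Before dose 1, a serum result from Day −45 to Day −3 is not enough, and a Day 0 urine test is added. At dose 2 the schedule accepts a pregnancy result three to four weeks old.

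**Result if the test is done before dose 2:** its age at dosing is 0 days.

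**How many women.** Planned enrolment is at most (4 + 5) × 3 = 27 patients of any sex. The number of women of child-bearing potential is not given.

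**The case against.** The best case on the other side is that the sponsor's intent is clear enough. Footnote k is explicit in both tables, the section devoted to pregnancy testing names Day 0 for the urine test, and 8.12 is worded to match. The 6.3.1.1 list is one merged list for two visits and is loosely drafted. On this view the item is an editorial slip, and adding a Day 0 limit to it would remove the conflict. That stands as an account of how the conflict arose. It does not give the dose 2 eligibility check a current result.

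Mitigation is also real. Two contraceptive methods are required, interval history is taken before each dose, a serum test follows any suspicion of pregnancy, and the closing note to the laboratory list in 7.2.7 allows testing at the investigator's discretion. None of these is a scheduled test before dose 2. The re-check itself does not mean every criterion is re-tested; hepatitis serology, for example, is not repeated. A urine test can also miss a very recent conception, so it narrows the gap without closing it.

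A reader might infer two stronger points that the documents do not support.

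- **That the lipid panel's Day 0 limit proves the pregnancy test was meant for both doses.** The same list includes measuring height with no day limit, although 7.2.1 and Table 1-1 place height at Screening only. A missing limit in this list is weak evidence of intent.
- **That a patient known to be pregnant could still be given dose 2, because 4.5.1 says only that the investigator may withdraw her.** Section 4.5.1 governs withdrawal from the study, not dosing. Sections 5.6 and 6.3.1.2, exclusion 1 and 7.2.7.8 already bar dose 2 after a known positive.

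**Conclusion.** The conflict is real and sits in current protocol text. Day 0 only may have been intended. If so, the gap applies at every site that follows the schedule: the last scheduled pregnancy result at dose 2 is 28 to 30 days old in 4-week cohorts (26 to 30 under the 6.3.1.3 window) and 21 to 23 days old in 3-week cohorts.

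These figures assume dosing within the printed windows and no test prompted by suspicion or ordered at discretion. They also assume that optional cohorts are dosed every 3 or 4 weeks, as the optional-cohort rules state. Section 6 still mentions intervals above 4 weeks, for which the result would be older. The number of women affected cannot be derived from the documents.

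This is a cheap improvement to patient safety and consistency. It does not touch any endpoint, the sample size or any analysis.

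**What to change.** Amend footnote k of Tables 1-1 and 12-1, and section 7.2.7.8, to require a urine pregnancy test pre-dose on Day 28 (Day 21 in 3-week cohorts) for women of child-bearing potential, with the result known before dosing. This matches 6.3.1.1 as printed. Keep the serum test on suspicion. Sections 4.5.1 and 8.12 need no change: dose 2 after a known positive is already barred, and 8.12 already covers reporting of a pregnancy found within 2 months of study drug. The SAP copies of the tables can follow at the next update.

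The cost is one urine strip per woman of child-bearing potential at a visit that already takes place. Urine is already collected pre-dose for PK, but the documents do not say that sample may be used for a strip, so a small extra portion may be needed. The change needs ethics committee and competent authority approval under 10.2.3, for up to 10 centers, and can be carried in the next amendment made for other reasons.
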